### 3.1.1.3 Overall Visit Response

Table 4 defines how the previously defined TL and NTL visit responses will be combined with new lesion information to give an overall visit response.

**Table 4 Overall Visit Responses**

TARGET	NON-TARGET	NEW LESIONS	OVERALL VISIT RESPONSE
CR	CR (or NA)	No (or NE)	CR
CR	Non-CR/Non-PD or NE	No (or NE)	PR
PR	Non-PD or NE or NA	No (or NE)	PR
SD	Non-PD or NE or NA	No (or NE)	SD
PD	Any	Any	PD
Any	PD	Any	PD
Any	Any	Yes	PD
NE	Non-PD or NE or NA	No (or NE)	NE
NA	CR	No (or NE)	CR
NA	Non-CR/Non-PD	No (or NE)	SD
NA	NE	No (or NE)	NE
NA	NA	No (or NE)	NED

CR complete response; PR partial response; SD stable disease; PD progression of disease; NE not evaluable; NA not applicable (only relevant if there were neither target nor non-target lesions at baseline); NED no evidence of disease.

## 3.2 Safety Variables

Safety and tolerability will be assessed in terms of AEs (including SAEs, AESIs), deaths, physical examinations, laboratory data, vital signs, ECGs and exposure. These will be collected for all patients throughout the study.

### 3.2.1 Primary Safety Endpoint

The primary endpoint of this study is the incidence of Grade 3 and Grade 4 TRAEs (see Section 3.2.3.1) which occur within the first six months (ie, up to and including the 183rd day) after the initiation of durvalumab. Any Grade 3 or Grade 4 TRAEs which started after the 183rd day of the study, or after the 90th day following discontinuation of durvalumab, or after the start of subsequent anti-cancer therapy will not be included. In the tables, listings and figures, the TRAEs are presented as “possibly related adverse events” as per the CRF and AZ standards.

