8.3.4 Adverse event data collection

The following variables will be collected for each AE:

- AE (verbatim)
- The date when the AE started and stopped
- The maximum CTCAE Grade reported

- Changes in CTCAE Grade (report only the maximum CTCAE Grade for the calendar day)
- Whether the AE is serious or not
- Investigator causality rating against the IPs (yes or no)
- Action taken with regard to IPs
- Administration of treatment for the AE
- Outcome

In addition, the following variables will be collected for SAEs:

- Date the AE met criteria for SAE
- Date the Investigator became aware of the SAE
- Seriousness criteria fulfilled
- Date of hospitalisation
- Date of discharge
- Probable cause of death
- Date of death
- Whether an autopsy was performed
- Causality assessment in relation to study procedure(s)
- Causality assessment in relation to other medication, as explained in Section 8.3.5
- Description of the SAE

The grading scales found in the revised NCI CTCAE version 4.03 will be utilised for all events with an assigned CTCAE grading. For those events without assigned CTCAE grades, the recommendation in the CTCAE criteria that converts mild, moderate, and severe events into CTCAE grades should be used. A copy of the CTCAE version 4.03 can be downloaded from the Cancer Therapy Evaluation Program website (<http://ctep.cancer.gov>).

It is important to distinguish between serious and severe AEs. Severity is a measure of intensity, whereas seriousness is defined by the criteria in [Appendix B, B 2](#). An AE of severe intensity need not necessarily be considered serious. For example, nausea that persists for several hours may be considered severe nausea, but not an SAE unless it meets the criteria shown in [Appendix B, B 2](#). On the other hand, a stroke that results in only a limited degree of disability may be considered a mild stroke, but it would be an SAE if it satisfies the criteria shown in [Appendix B, B 2](#).

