9.2 Sample size determination

The primary objective of this study is to assess the safety and tolerability of durvalumab (MEDI4736) which is defined as Grade 3 and Grade 4 TRAEs observed within 6 months after the initiation of durvalumab (MEDI4736) treatment. In addition, safety and tolerability of durvalumab (MEDI4736) will be characterized for the cohorts of WHO/ECOG PS 0 to 1 and 2 patients.

This is a safety study and no formal sample size calculation will be done. Between 100 and 120 patients will be enrolled in the WHO/ECOG PS 0 to 1 Cohort and up to 30 patients in the WHO/ECOG PS 2 Cohort depending on recruitment. CCI

CCI

CCI

CCI

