### **3.2.3 Adverse Events**

Details of all AEs and SAEs will be collected for a patient from the signing of the informed consent form (ICF) up to 90 days after the last dose of durvalumab. If an event starts after this period and the Investigator considers that it is possible that it is due to a late onset toxicity to durvalumab, then it should be reported as an AE or SAE.

All AEs will be coded using the latest version of Medical Dictionary for Regulatory Activities (MedDRA) providing the System Organ Class (SOC) and Preferred Term (PT).

In addition, all AEs will also be graded according to the National Cancer Institute (NCI) Common Terminology Criteria for AEs (CTCAE Version 4.03) allocating grades from Grade 1 to Grade 4 which will be used for the reporting. The meaning of these categories are as follows:

- Grade 1: Mild AE
- Grade 2: Moderate AE
- Grade 3: Severe AE
- Grade 4: Life-threatening or disabling AE
- Grade 5: Death related to AE

Treatment-emergent adverse events (TEAEs) are AEs that start after the first dose of durvalumab or which start prior to the first dose of durvalumab but worsen following the first dose of durvalumab, and where the start date/date of worsening is also no later than 90 days after the last dose of durvalumab or the initiation of the first subsequent therapy following discontinuation of durvalumab (whichever occurs first). Any TEAE will be included in the AE summaries as detailed in Section 4.5.1.

Missing start and stop dates for AEs will be imputed using the rules described in Section 4.1.3.

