#### **3.2.3.1 Treatment-Related Adverse Events**

A TRAE is any AE with a relatedness to durvalumab of possible or probable, or where the

relatedness is missing. When the relatedness of an AE is missing on the eCRF, all efforts will be taken to ensure that the Investigator assigns his/her assessment of relatedness prior to database lock. In the tables, listings and figures, the TRAEs are presented as “possibly related adverse events” as per the CRF and AZ standards.

If relatedness of an AE is missing at the DBL, as given in Section 4.1.2, the AE will be considered as related to durvalumab.

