### **3.2.3.3 Immune-Mediated Adverse Event**

An imAE is defined as an AESI that is associated with drug exposure and is consistent with an immune-mediated mechanism of action and where there is no clear alternate etiology. In general, imAEs will include AESIs that are managed using steroids, immunosuppressants and/or hormone replacement therapy.

This document comprises the specification for the analysis of the imAEs as identified by the investigator (as recorded in CRF Adverse Events (AE)).

Time to event analyses for imAEs will be performed for the following definitions:

- Time to first onset of imAE: Start date of first imAE episode – First dose date + 1
- Time to first onset of imAE of Grade 3 or 4: First date of imAE episode that had CTCAE Grade 3 or 4 – First dose date + 1
- Time to resolution of imAE: End date of imAE episode – Start date of imAE episode + 1
- Time to resolution of Grade 3 or 4: End date of imAE episode that had CTCAE Grade 3 or 4 – First date imAE episode had severity of grade 3 or higher + 1

If an imAE does not resolve, then the time to resolution will be censored at earliest date of DCO, death date, or last dose date + 90 days. Patients who die prior to resolution of the imAE will be censored at the date of death.

Adjudication and statistical analysis for the imAEs will be performed by AstraZeneca. The results will be incorporated into and discussed in the CSR.

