### **4.3 Analysis of Primary Safety Endpoint**

The primary endpoint of this study is the incidence of Grade 3 and Grade 4 TRAEs (see Section [3.2.3.1](#)) which occur within the first six months (ie, up to and including the 183rd day) after the initiation of durvalumab. Any Grade 3 or Grade 4 TRAEs which started after the 183rd day of the study, or after the 90th day following discontinuation of durvalumab, or after the start of

subsequent anti-cancer therapy will not be included.

The number and percentage (and exact Clopper-Pearson 95% CI) of patients with NCI CTCAE Grade 3 or Grade 4 TRAEs, both overall and for those occurring within the first six months after initiation, will be summarized for the SAF for all patients and within the WHO/ECOG PS 0/1 and PS 2 groups. This summary will also be graphically presented as a bar chart. The number and percentages of patients with NCI CTCAE Grade 3 or Grade 4 TRAEs will also be summarized by SOC and PT.

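### The primary safety endpoint stops at Grade 4, so a patient whose only severe treatment-related event is fatal counts as event-free, and no planned output gives the six-month Grade 3-5 rate with a confidence interval

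*SAP*

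**What the plan says.** SAP 3.2.1 defines the endpoint: "The primary endpoint of this study is the incidence of Grade 3 and Grade 4 TRAEs", with a window from first dose through Day 183. SAP 4.3 repeats this. It plans a percentage with a Clopper-Pearson 95% interval, based on the number "of patients with NCI CTCAE Grade 3 or Grade 4 TRAEs, both overall and for those occurring within the first six months after initiation", for all treated patients and for each PS group. The protocol has the same restriction. Its section 9.2 describes the primary objective through "Grade 3 and Grade 4 TRAEs observed within 6 months after the initiation of durvalumab (MEDI4736) treatment".

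On grading, SAP 3.2.3 speaks of "allocating grades from Grade 1 to Grade 4 which will be used for the reporting", and then lists Grade 5 (death) directly underneath. Protocol 9.5.1, on the primary variable, summarises safety data by maximum CTCAE grade.

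On timing, SAP 3.2.1 includes events that *occur* by Day 183 and excludes those that *started* later. It does not say which date is meant. For immune-mediated events, SAP 3.2.3.3 is explicit: onset of a severe episode is the "First date of imAE episode that had CTCAE Grade 3 or 4". Protocol 8.3.4 collects the data needed for such a rule: "Changes in CTCAE Grade (report only the maximum CTCAE Grade for the calendar day".

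Fatal TRAEs appear in SAP 4.5.1, as a line in the overall AE summary and in a table by system organ class and preferred term.

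**The concern.** The endpoint is meant to summarise severe drug toxicity, yet the most severe grade does not contribute to it. Protocol 4.2.1 gives as reasons for the study the need for more data on severe events, the possible interaction of radiotherapy with pneumonitis, and the thin evidence in the PS groups studied. Someone who reads the primary rate as the six-month rate of severe toxicity would be reading a figure in which a treatment-related death can count as no event. The PS 2 cohort has at most 30 patients, so a single reclassified patient is visible in the estimate.

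**Working it through.** **1. The plan's own intervals.** The Clopper-Pearson limits for x events in n patients are: lower = 0.025 quantile of Beta(x, n-x+1); upper = 0.975 quantile of Beta(x+1, n-x). Using the counts in SAP 1.3:

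- 10/120 = 8.3%: 4.1 to 14.8 (SAP: 4.1 to 14.8)
- 12/100 = 12.0%: 6.4 to 20.0 (SAP: 6.4 to 20.0)
- 4/30 = 13.3%: 3.8 to 30.7 (SAP: 3.8 to 30.7)

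In SAP Table 1, 13 of 15 intervals match to one decimal. The other two each have one limit off by 0.1 point (8/100 upper: 15.2 against 15.1; 15/100 lower: 8.6 against 8.7), which is immaterial.

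**2. Effect of Grade 5-only patients.** The documents give no fatal-TRAE rate, so one to three such patients is an assumed range. One patient is worth 1/120 = 0.8 points or 1/30 = 3.3 points. At the protocol's ceiling of 150 treated patients it would be 1/150 = 0.7 points.

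| Added patients | n=120, from 10 | n=30, from 4 |
|---|---|---|
| 0 | 8.3% (4.1-14.8) | 13.3% (3.8-30.7) |
| 1 | 9.2% (4.7-15.8) | 16.7% (5.6-34.7) |
| 2 | 10.0% (5.3-16.8) | 20.0% (7.7-38.6) |
| 3 | 10.8% (5.9-17.8) | 23.3% (9.9-42.3) |

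**3. Can the planned tables recover the Grade 3-5 rate?** Suppose the Grade 3/4 line shows 10 of 120 and the fatal-TRAE line shows 3. A patient may have both a Grade 3/4 event and a fatal one, so the number with either lies between 10 and 10 + 3 = 13, that is 8.3% to 10.8%. With 4 and 3 in the PS 2 cohort, it lies between 4 and 7 of 30, that is 13.3% to 23.3%. The fatal line also has no Day 183 cut. In SAP 4.5.1, the maximum-grade table and the table of common events at Grade 3 or higher are specified for AEs of any causality, and the latter leaves out terms below a frequency threshold. The protocol 9.4 outcomes by causality and severity carry no six-month cut or CI.

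**4. Events that progress to death.** If an event is classified by its maximum grade, one that reached Grade 3, then 4, then 5 is a Grade 5 event and leaves the numerator. If the recorded grade changes are used, it can count through its Grade 3/4 phase. SAP 3.2.1 and 4.3 do not choose.

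**5. The event date.** If *started* means AE onset and the event carries its maximum grade, an event with low-grade onset before Day 183 that becomes severe afterwards is counted. If it means the start of the Grade 3/4 phase, that event is excluded. Moving an assumed one to three such patients out of 10/120 gives 7.5% (3.5-13.8), 6.7% (2.9-12.7) or 5.8% (2.4-11.6). This acts in the opposite direction to step 2.

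**The case against.** Grade 3/4 is not a slip. Protocol and SAP use it consistently, and it is the metric that protocol 2.2.1 reports for treatment-related events in the earlier pivotal study. The result will be labelled as Grade 3/4 incidence and will estimate exactly that. Fatal TRAEs, fatal events of special interest, fatal immune-mediated events and all deaths have their own summaries, and SAP 4.1.1 has safety data shown by PS group. No hypothesis is tested and no stated threshold depends on the rate. All of this stands. It is why the primary should not be replaced, and why it would be wrong to infer that fatal events go unreported or that the SAP departs from the protocol. It does not supply the missing combined six-month rate.

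Two stronger readings are tempting. The first is that the SAP counts worsening after Day 183 as a six-month event. It does not say so: the subject of *started* is the Grade 3/4 TRAE, and the same section also uses *occur*. What the text supports is an undefined event date.

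The second is that the TRAE filter misses the collected data, because SAP 3.2.3.1 says "A TRAE is any AE with a relatedness to durvalumab of possible or probable" while protocol 8.3.4 collects "Investigator causality rating against the IPs (yes or no". The yes/no question asks about a reasonable possibility of causation, and the SAP treats missing causality as related. The only workable filter is therefore *yes or missing*, and no patient changes category.

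**Conclusion.** The gap in reporting is real; its size is unknown in advance. As defined, the sole primary endpoint gives no event to a patient whose only severe TRAE is graded 5, and it leaves open how an event progressing to Grade 5 is treated. No planned output gives the incidence of Grade 3-5 TRAEs within 183 days with a CI, and it cannot be rebuilt from the planned lines. The effect is 0.8 points per patient at n=120 and 3.3 points at n=30. The starting counts are the SAP's own illustrations, and the number of added patients is an assumption. Only the estimate is affected; no test, error rate or power depends on it. The undefined event date is a secondary clarification, and the causality wording is an editorial note.

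**What to change.** Keep Grade 3/4 within 183 days as the primary endpoint, so that the comparison with the earlier pivotal study is preserved. In SAP 3.2.1 and 4.3:

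- Add, beside the primary result, the number and percentage of patients with any Grade 3-5 TRAE within 183 days, with exact 95% CI, overall and by PS cohort.
- State that an event progressing to Grade 5 counts.
- Apply the Day 183 cut to the first date on which the TRAE was Grade 3 or higher, derived from the recorded grade changes and in line with the SAP's rule for onset of severe immune-mediated events.

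In SAP 3.2.3, correct the reported grade range so that it agrees with the Grade 5 entry listed below it. In SAP 3.2.3.1, define a TRAE as causality answered yes or missing.

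No new data are needed. The cost is SAP wording, one derivation and one extra row per table. The sponsor would show a headline toxicity rate that may be slightly higher: the Grade 3-5 count cannot be below the Grade 3/4 count when both use the same dating rule.

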3 OBJECTIVES AND ENDPOINTS

The study objectives and corresponding endpoints/variables are listed in [Table 3](#).

Table 3 Study objectives

| OBJECTIVE | ENDPOINT/VARIABLE |
|--|--|
| PRIMARY OBJECTIVE | |
| To assess the safety and tolerability profile of durvalumab (MEDI4736) as defined by Grade 3 and Grade 4 TRAEs ^a within 6 months from the initiation of durvalumab (MEDI4736) treatment | Grade 3 or Grade 4 TRAEs ^a |
| SECONDARY OBJECTIVES | |
| Efficacy objectives | |
| To assess the efficacy of durvalumab (MEDI4736) treatment in terms of PFS and OS | Median PFS according to RECIST 1.1 as assessed by the Investigator |
| | Median PFS12 and PFS24 according to RECIST 1.1 as assessed by the Investigator |
| | Median OS, OS12, OS24, and OS36 |
| To further assess the efficacy of durvalumab (MEDI4736) treatment in terms of ORR and DoR | ORR according to RECIST 1.1 as assessed by the Investigator |
| | DoR according to RECIST 1.1 as assessed by the Investigator |
| To assess the efficacy of durvalumab (MEDI4736) treatment in terms of lung cancer mortality | Lung cancer mortality |

| OBJECTIVE | ENDPOINT/VARIABLE |
|---|--|
| Secondary safety objective | |
| To further assess the safety and tolerability profile of durvalumab (MEDI4736) treatment, including all AEs | AEs, SAEs, AESIs, imAEs, physical examinations, vital signs including BP, pulse, temperature, and respiratory rate; ECGs, and laboratory findings including clinical chemistry, haematology and urinalysis |
| EXPLORATORY OBJECTIVES | |
| CCI [REDACTED] | CCI [REDACTED] |
| CCI [REDACTED] | CCI [REDACTED] |
| CCI [REDACTED] | CCI [REDACTED] |
| CCI [REDACTED] | CCI [REDACTED] |
| CCI [REDACTED] | CCI [REDACTED] |
| CCI [REDACTED] | CCI [REDACTED] |

a. TRAEs and PRAEs are used interchangeably and PRAEs will be reported in the SAP, Tables, Figures, and Listings, and CSR.

Note: Toxicities will be classified as per CTCAE grading system NCI CTCAE version 4.03. Analysis of ORR and DoR will be based upon Investigator assessment according to RECIST 1.1. Prior irradiated lesions may be considered measurable and selected as TLs providing they fulfil the other criteria for measurability.

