4.4 End of study definition

The end of the study is defined as the last visit of the last patient undergoing the study. A patient is considered to have completed the study when he/she has completed his/her last study visit per protocol.

The final DCO is planned to occur when the last patient had the opportunity to receive durvalumab (MEDI4736) for a maximum of 24 months, followed by a 90-day safety follow-up period post the last dose of IP.

At the final DCO, the clinical study database will close to new data. However, patients will be permitted to continue to receive IP beyond the closure of the database if a rollover or safety extension study is available at the time of the final DCO and, in the opinion of the Investigator, they are continuing to receive benefit from IP. For patients who do continue to receive IP beyond the time of the final DCO, Investigators will continue to report all SAEs to AstraZeneca Patient Safety until 90 days after last IP dose, in accordance with Section 8.4.1. If an Investigator learns of any SAEs, including death, at any time after a patient has completed the study, and he/she considers there is a reasonable possibility that the event is causally related to the study drug, the Investigator should notify AstraZeneca Patient Safety.

Any SAE or non-serious AE ongoing at the time of this final DCO is to be followed up at the discretion of the Investigator and per local practice and in alignment with the Dosing Modification and Toxicity Management Guidelines (Section 8.4.5), unless the event is considered by the Investigator to be unlikely to resolve or the patient is lost to follow-up.

See [Appendix A, A 6](#) for guidelines for the dissemination of study results.

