At the time of the final DCO, the analysis portion of the clinical study will have been completed and all patients remaining in the study will be considered to have completed the analysis portion of the study. At the time of final DCO, the clinical study database will be closed to new data.

Patients in OS follow-up (progressed and have discontinued treatment) will be considered to have completed the study.

Patients who are receiving treatment at the time of final DCO may continue receiving IP if the Investigator judges that they are gaining clinical benefit.

All patients will receive scans and follow-up care in accordance with standard local clinical practice. All data will be recorded on patient charts but will not otherwise be reported for the purposes of this study.

For patients who do continue to receive IP beyond the time of the final DCO, Investigators will report SAEs to AstraZeneca Patient Safety via paper case report forms (CRFs) until 90 days after the last dose of study drug, in accordance with Section 8.4.1. Any SAE or non-serious AE ongoing at the time of the DCO is to be followed up at the discretion of the Investigator and per local practice and in alignment with the Dosing Modification and Toxicity Management Guidelines (Section 8.4.5), unless the event is considered by the Investigator to be unlikely to resolve, or the patient is lost to follow-up. Data will not be captured for the purposes of this study outside of being recorded in the patients' source documents.

Following the DCO, SAE reporting applies only to patients who are active on IP and within 90 days after the last dose; in all other cases, only a Statement of Death notification is to be sent to AstraZeneca.

Different drug supply options will be available depending on the country, and these will be proposed to the patient when the most appropriate alternatives for continued treatment have been agreed between AZ and the investigator. Options may include the participation in a new rollover study or, if the study drug has been locally approved for use in this disease indication, patients may be discontinued and switched to the marketed product, in accordance with local laws.

In the event that a rollover or safety extension study is available at the end of 24 months of study treatment, or at the time of the final DCO / database closure, patients currently receiving

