8.3.1 Method of detecting adverse events and serious adverse events

Care will be taken not to introduce bias when detecting AEs and/or SAEs. Open-ended and non-leading verbal questioning of the patient is the preferred method to inquire about AE occurrences.

8.3.2 Time period and frequency for collecting adverse event and serious adverse event information

AEs and SAEs will be collected from time of signature of informed consent throughout the treatment period and including the follow-up period (90 days after the last dose of IP). If an event that starts post the defined safety follow-up period noted above is considered to be due to a late-onset toxicity to study drug then it should be reported as an AE or SAE, as applicable.

All SAEs will be recorded and reported to the Sponsor or designee within 24 hours, as indicated in [Appendix B](#). The Investigator will submit any updated SAE data to the Sponsor within 24 hours of the data being available.

Investigators are not obligated to actively seek AE or SAE in former study patients. However, if the Investigator learns of any SAE, including a death, at any time after a patient's last visit and he/she considers the event to be reasonably related to the study drug or study participation, the Investigator may notify the Sponsor.

The method of recording, evaluating, and assessing causality of AE and SAE and the procedures for completing and transmitting SAE reports are described in [Appendix B](#).

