### 1.1 Study Objectives

#### 1.1.1 Primary Objective

Primary Objective	Endpoint / Variable
To assess the safety and tolerability profile of durvalumab as defined by Grade 3 and Grade 4 treatment-related adverse events (TRAEs a ) within six months from the initiation of durvalumab treatment	Grade 3 and Grade 4 TRAEs a

Note: Toxicities will be classified as per CTCAE grading system NCI CTCAE version 4.03.

TRAE: treatment-related adverse event; CTCAE: Common Terminology Criteria for Adverse Event; NCI: National Cancer Institute.

a. TRAEs and PRAEs are used interchangeably and "possibly related adverse events" (PRAEs) will be reported in this SAP, tables, figures, listings, and CSR.

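### The primary Grade 3/4 TRAE rate omits related events that start before Day 183 but after the 90-day or next-therapy cut, and no sensitivity analysis is planned for them

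*SAP*

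**What the plan says.** Protocol Section 3 defines the primary objective by Grade 3 and 4 TRAEs "within 6 months from the initiation of durvalumab (MEDI4736) treatment", and SAP 1.1.1 repeats it ("within six months from the initiation of durvalumab treatment"). Neither mentions a cut at the end of treatment or at next therapy.

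SAP 3.2.1 and 4.3 count TRAEs "which occur within the first six months (ie, up to and including the 183"rd day). They then exclude TRAEs starting after the 90th "day following discontinuation of durvalumab, or after the start of subsequent anti-cancer therapy will not be included". SAP 4.3 reports a simple percentage of the safety analysis set with a Clopper-Pearson interval. That set is everyone who received at least one dose (Protocol 9.3.1, SAP 2.1.1).

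Collection follows a different rule from counting:
- Routine AE collection runs to 90 days after the last dose (Protocol 8.3.2, SAP 3.2.3).
- The protocol synopsis, on follow-up after discontinuation, includes patients who have started another anticancer therapy in that 90-day AE follow-up.
- After 90 days, an event "considered to be due to a late-onset toxicity to study drug then it should be reported as an AE or SAE" (Protocol 8.3.2), although sites need not look for such events.
- Protocol 9.5.2.1 puts AEs beyond 90 days in a separate listing and keeps them out of the AE summaries.

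**The concern.** The objective's clock starts at the first dose and ends at six months. The counting rule adds two earlier stops, and both depend on when the patient leaves treatment. A patient cut off before Day 183 is counted as event-free for the rest of the window, because the estimator is a crude proportion with no censoring or time at risk.

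Protocol 4.2.1 justifies the six-month window by literature placing most immune-mediated events within 3 to 6 months of starting treatment. For a patient who receives one dose, the endpoint closes at about month 3.

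At stake is the trial's main product. There is no hypothesis test (Protocol 9.1), so what readers will take away is this one descriptive rate, overall and by performance status (PS) cohort. The confidence interval does not reflect the omission.

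**Working it through.** **1. The plan's own precision.** SAP 1.3 gives 10/120 = 8.3% with a 95% interval of 4.1% to 14.8%, 12/100 with 6.4% to 20.0%, and 4/30 with 3.8% to 30.7%. Exact Clopper-Pearson limits reproduce all three. The half-width at 10/120 is (14.8 − 4.1)/2 = 5.35 points.

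**2. Days outside the endpoint under the 90-day cut.** Cycles are 28 days (Protocol 1.2), so doses fall on Days 1, 29, 57, 85 and 113. The discontinuation date is taken as the last-dose date. Gap = max(0, 183 − (last dose day + 90)).

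| Last dose | Coverage ends | Gap (days) | Share of 183 |
|---|---|---|---|
| Day 1 | Day 91 | 92 | 50% |
| Day 29 | Day 119 | 64 | 35% |
| Day 57 | Day 147 | 36 | 20% |
| Day 85 | Day 175 | 8 | 4% |
| Day 113 | Day 203 | 0 | 0% |

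The 90-day cut therefore affects only patients whose last dose is on or before Day 92. The next-therapy cut can affect anyone who starts other treatment before Day 183.

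**3. Person-time.** If early stoppers are spread evenly over doses 1 to 4, the mean gap is (92 + 64 + 36 + 8)/4 = 50 days. With a share f of patients stopping by dose 4, the lost person-time is f × 50/183: 2.7% at f = 10% and 10.9% at f = 40%. The documents give no early-stopping rate, so this range for f is an assumption.

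**4. Effect on the rate.** Assume a constant hazard giving true risk p over 183 days: h = −ln(1 − p)/183. Counted risk = (1 − f)p + f × mean[1 − exp(−h·c)], where c is the number of covered days.

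Example: p = 12%, f = 20%, stoppers even over doses 1 to 4. Then h = 0.1278/183 = 0.000699 per day. For c = 91, 119, 147 and 175 the risks are 6.2%, 8.0%, 9.8% and 11.5%, with mean 8.85%. Counted risk = 0.8 × 12 + 0.2 × 8.85 = 11.4%, a loss of 0.6 points.

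Loss in percentage points, with patients per 120 in brackets:

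| Scenario | p = 8.3%, f = 10% | p = 8.3%, f = 40% | p = 12%, f = 10% | p = 12%, f = 40% |
|---|---|---|---|---|
| 90-day cut, stops even over doses 1–4 | 0.2 (0.3) | 0.9 (1.1) | 0.3 (0.4) | 1.3 (1.5) |
| 90-day cut, all stop after dose 1 | 0.4 (0.5) | 1.6 (2.0) | 0.6 (0.7) | 2.3 (2.8) |
| Next therapy 30 days after last dose, doses 1–4 | 0.5 (0.6) | 2.0 (2.4) | 0.7 (0.9) | 2.8 (3.4) |

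The 30-day timing is also an assumption.

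**5. Late related SAEs, side by side.** This does not bear on the Day-183 endpoint.
- Protocol 8.3.2, related SAE after the last visit: "the Investigator may notify the Sponsor".
- Protocol 4.4, related SAE after study completion: "the Investigator should notify AstraZeneca Patient Safety".
- Protocol 8.3.11: a death after the safety follow-up that results from late-onset toxicity is to be reported as an SAE as well.
- Protocol 4.1 and 6.1.3: after data cut-off, SAE reporting is tied to being on study drug or within 90 days of the last dose, and 6.1.3 adds that "in all other cases, only a Statement of Death notification is to be sent to AstraZeneca".

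These passages do not give one rule for a related SAE that starts late.

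**The case against.** The cut is a deliberate treatment-emergent window, pre-specified and used consistently (Protocol 9.5, SAP 3.2.3 and 4.5.1). With the half-life of about 21 days in Protocol 4.3.1, 90 days is over four half-lives. Stopping the count at next therapy protects attribution. These points stand, and they are reasons to leave the headline definition alone.

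A patient who stops because of a Grade 3/4 TRAE is already a primary event, so truncation cannot change that patient's status. Progression is not the same as stopping either, since Protocol 6.1.3 allows treatment through progression. Both points stand. They are why no share of affected patients can be derived from progression or AE-discontinuation figures.

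SAP 4.5.1 already plans a summary of TRAEs within 90 days of the last dose that ignores next therapy. That helps only in part: it is not limited to Grade 3/4 or to Day 183, and it too ends at 90 days.

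The bias is also small beside the sampling error. That is true of the overall rate and limits how much change is warranted. One event in a PS 2 cohort of 30 is, however, 1/30 = 3.3 points.

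**Conclusion.** The point holds in a limited form. The endpoint as counted is narrower than the objective as stated. The rule only removes events from the numerator, so any bias is downward. Some related Grade 3/4 events by Day 183 will be collected yet appear neither in the primary rate nor in any planned sensitivity analysis.

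The size is about 0.3 to 3.4 patients per 120, or 0.2 to 2.8 points, against a half-width of about 5.4 points. This rests on 10% to 40% stopping by dose 4, a true risk of 8.3% to 12%, and a constant hazard that is the same after stopping. If related events become rarer off drug, the loss is smaller. Patients who stop later but start other therapy before Day 183 are not in the range and would add to it.

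A reader might infer three stronger things that the documents do not support:
- That AE collection stops at next therapy. It continues to 90 days after the last dose; the endpoint and most summaries stop.
- That time beyond 90 days is unobserved. Follow-up there is passive, not absent.
- That the protocol lets a late related death escape SAE reporting. Protocol 8.3.11 asks for it. The defect is that other passages conflict.

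**What to change.** Keep the primary definition. In SAP 4.3, add:

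1. A sensitivity analysis counting every reported Grade 3/4 TRAE with onset by Day 183, whatever the 90-day limit or subsequent therapy, overall and by PS cohort, with the same exact interval.
2. The number and percentage of patients with AE follow-up to Day 183, overall and by PS cohort. The sensitivity count still depends on passive reporting beyond 90 days, and this shows how far it can be trusted.

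The cost is a little more programming on data already collected. The downside is a few events after next-line therapy with less certain attribution, which stay out of the headline rate.

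Separately, reconcile Protocol 4.1, 4.4, 6.1.3, 8.3.2 and 8.3.11 so that one rule covers related SAEs after the last visit or data cut-off. This is a wording change to the protocol and leaves the primary endpoint untouched.
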